8.6.2 Completion of the Study

The Investigator will document the completion or the reason for early withdrawal by a subject in the case report form. The following categories should be used to describe the early withdrawal reasons in the case report form:

- Subject discretion (document reason)
- Investigator considers it to be in the best interest of the subject (document reason)
- Adverse event(s)
- Administrative reasons (e.g., early termination of the study)
- Subject lost to follow-up
- Major protocol violation (with approval by the Sponsor)
- Death

If the study is prematurely terminated by Conatus, all reasonable attempts should be made to complete the final follow-up phase for all remaining subjects.

8.6.3 Termination of the Study

The study may be terminated prematurely, for any reason, by the Investigator with sufficient advance notice, per the terms of the contract with the Sponsor. The reason should be communicated in writing to the Sponsor.

Title: A Multicenter, Double-Blind, Randomized Trial of IDN-6556 in Subjects Who had Hepatitis C Virus (HCV) Reinfection and Liver Fibrosis or Cirrhosis following Orthotopic Liver Transplantation for Chronic HCV Infection and Who Subsequently Achieved a Sustained Virologic Response Following anti-HCV Therapy

Conatus reserves the right to discontinue the study at any time for clinical or administrative reasons. Such a termination must be implemented by the Investigator, if instructed to do so by Conatus, in a time frame that is compatible with each subjects' well-being.

9.0 INVESTIGATIONAL MEDICINAL PRODUCT

For the purpose of this protocol the term 'investigational medicinal product (IMP)' is interchangeable with the term 'study medication' and/or 'study drug'.

All study medication (IDN-6556 and matching placebo) will be manufactured according to Good Manufacturing Practice (GMP).

9.1 IDN-6556 and Placebo Supplies

The double-blind supplies of IDN-6556 will be in bottles containing 60 capsules, with each capsule containing 25 mg of IDN-6556. Matching placebo will also be supplied in bottles containing 60 capsules. Therefore, each bottle will contain a 30-day supply of study drug (IDN-6556 or placebo).

Subjects should be instructed to take one capsule in the morning and one capsule in the evening, preferably with food.

IDN-6556 and placebo supplies must be stored in a secure, lockable area. Subjects should be instructed to store their study drug bottles with the caps tightly closed in a safe area at room temperature. Study drug bottles should not be stored near heating devices, at high temperatures or humidity, or where children or pets have access to them.

9.2 Investigational Medicinal Product Packaging and Labeling

The packaging and labeling of study medication supplies will be performed according to GMP standards by a designated, qualified vendor.

IDN-6556 and placebo capsules will be dispensed to subjects in the provided bottles in sufficient quantities for continuation of treatment to at least the next scheduled visit, along with instructions for the proper method of taking the study drug.

All study drug bottles will carry a uniquely numbered label which will also contain the drug description and conditions for storage.

Title: A Multicenter, Double-Blind, Randomized Trial of IDN-6556 in Subjects Who had Hepatitis C Virus (HCV) Reinfection and Liver Fibrosis or Cirrhosis following Orthotopic Liver Transplantation for Chronic HCV Infection and Who Subsequently Achieved a Sustained Virologic Response Following anti-HCV Therapy

9.3 Investigational Medicinal Product Dispensing and Accountability

All study drugs must be dispensed in the original containers in order to assure stability of the drugs. At each visit, subjects must be instructed to return all, original, study-drug containers (even empty containers) and all unused capsules (in partially or completely full bottles) in order to adequately assess each subject's compliance with dosing instructions. The number of capsules remaining in the bottles should be counted at each visit to assess subject compliance with study drug administration. Every effort should be made to obtain all unused capsules and all dispensed bottles.

9.4 Investigational Medicinal Product Administration

Subjects will be instructed to take IDN-6556 or placebo twice daily, about the same time in the morning and evening, preferably with food.

Details of dosing information (e.g., dates of dosing, missed doses and dose adjustment, if any) are to be captured in the case report forms.

10.0 WARNINGS AND PRECAUTIONS

IDN-6556 has potential to be teratogenic (refer to the Investigator's Brochure for further details). There have been no studies with this compound in pregnant women. Teratology studies, conducted in rats and rabbits, demonstrated that IDN-6556 may be teratogenic. Therefore, IDN-6556 should not be used in pregnant women. IDN-6556 has also been found to reduce male and female fertility in rats. There have been no studies on the effect of IDN-6556 on fertility in men and women.

Both male and female subjects of reproductive potential must use two reliable forms of contraception from screening to one month after the last dose of study drug. Effective contraception is defined as abstinence or two reliable forms of contraception, including one barrier method, used simultaneously.

If pregnancy occurs in a female subject taking study drug, the subject should be instructed to immediately stop taking the study drug, and the Investigator should inform the Sponsor within 24 hours of the Investigator's learning of the pregnancy. If the female subject is in the Double-Blind Phase of the study, the treatment arm may be unblinded (after discussion between the Investigator and the Conatus Medical Monitor). If the female subject chooses to terminate the pregnancy, the Investigator should document the termination and contact the Conatus Medical Monitor to discuss whether continued participation of the subject in the study is appropriate. If the female subject chooses to continue the pregnancy, the procedures for withdrawing a subject from the study should be completed, and the

Title: A Multicenter, Double-Blind, Randomized Trial of IDN-6556 in Subjects Who had Hepatitis C Virus (HCV) Reinfection and Liver Fibrosis or Cirrhosis following Orthotopic Liver Transplantation for Chronic HCV Infection and Who Subsequently Achieved a Sustained Virologic Response Following anti-HCV Therapy

Investigator will attempt to obtain information on the outcome of the pregnancy. If the pregnancy goes to term, then the Investigator should also attempt to obtain information on the health of the infant after delivery and provide the information to the Sponsor.

If pregnancy occurs in a female subject after the Double-Blind Phase of the study but within one month of taking study drug, the Investigator should inform the Sponsor immediately.

If pregnancy occurs in the female partner of a male subject during the Double-Blind Phase of the study or within one month of taking study drug, the Investigator should inform the Sponsor immediately.

11.0 DOCUMENTATION OF DATA

11.1 Source Documentation

All data obtained in this study are source data. The clinical site study staff members will record the data on source documents immediately, except for data that are available on original printouts or as data files.

All clinical work conducted under this protocol will be conducted according to GCP rules. This includes an inspection by the Sponsor or their designee(s) and/or health authority representative(s) at any time. The Investigator will agree to the inspection of study-related records by representatives of the health authority(ies) and/or the Sponsor. If the study is to be audited by a health authority at a given site, the Investigator will agree to immediately notify the Sponsor upon receipt of the audit notification.

11.2 Data Entry in Database

All data will be entered electronically by the study personnel using electronic data capture (EDC) specifically designed for this study.

11.3 Query Checks

The raw data will be checked by appropriate programs for consistency and plausibility according to previously defined query checks documented in a data validation plan.

Title: A Multicenter, Double-Blind, Randomized Trial of IDN-6556 in Subjects Who had Hepatitis C Virus (HCV) Reinfection and Liver Fibrosis or Cirrhosis following Orthotopic Liver Transplantation for Chronic HCV Infection and Who Subsequently Achieved a Sustained Virologic Response Following anti-HCV Therapy

11.4 Coding of Adverse Events, Drugs, and Diseases

After data entry, the AEs will be coded according to the MedDRA dictionary. Concomitant medications will be coded according to the World Health Organization Drug Reference List.

11.5 Study Language & Translations

The primary study materials (protocol, correspondence, clinical study report) will be prepared in English. However, where the first language of the subject, study personnel, or others involved in the study (such as IRBs/IECs) is not English, appropriate arrangements will be made to have the relevant documents translated into the local language. In this case, the qualified translator will need to provide documentation to attest to the fact that the translated study documents are an accurate reflection of the original, English study documents.

Additional documents may need to be translated into English (e.g., transcripts of necessary additional hospital tests that may occur), and others (e.g., new safety information) may need to be translated into the local language. The Sponsor, or designee, will make arrangements for such translations to occur promptly.

12.0 STATISTICAL METHODS

12.1 Introduction

Detailed methodology for summary and statistical analyses of the data collected in this study will be documented in a Statistical Analysis Plan (SAP), which will be dated and maintained by the sponsor. This document may modify the plans outlined in the protocol.

Should any of the assumptions of the statistical methods described below not be met, alternative methods will be applied and documented in the Clinical Study Report.

12.2 Parameters of Interest

12.2.1 Safety Variables

The following parameters will be recorded for the safety evaluation:

- Adverse events
- Vital signs (pulse, heart rate, respiration), physical examinations
- Clinical chemistry, hematology, coagulation, and urinalysis

Title: A Multicenter, Double-Blind, Randomized Trial of IDN-6556 in Subjects Who had Hepatitis C Virus (HCV) Reinfection and Liver Fibrosis or Cirrhosis following Orthotopic Liver Transplantation for Chronic HCV Infection and Who Subsequently Achieved a Sustained Virologic Response Following anti-HCV Therapy

- ECGs
- Liver and abdominal ultrasounds

12.2.2 Efficacy Variables

The following parameters will be recorded for the efficacy evaluation:

- Histologic changes defined as ≥ 1 point change in the Ishak Fibrosis Score
- Effects on liver inflammation in the necro-inflammatory sub-score of the modified Histological Activity Index. A responder will be defined as a subject who has improved by at least 2 points at 24 months on the necro-inflammatory sub-score of the modified Histological Activity Index from Baseline.
- Clinical outcomes defined as time to clinical worsening. Time to decompensation, re-transplantation, and/or death will be captured as clinical outcomes. (Note: Decompensation is defined as presence of: bleeding varices, encephalopathy, ascites requiring treatment and jaundice.)
- Effects on biomarkers of apoptosis and mechanism of action
- Effects on liver function parameters such as ALT, AST, bilirubin
- Changes in transient elastography (at select centers)

12.2.3 Other Variables

The following parameter will be assessed as an exploratory variable:

- Effects on liver collagen as measured by morphometric image analysis

12.3 Demographics and Baseline Characteristics

All continuous parameters will be summarized using standard summary statistics as appropriate (n, mean, standard deviation, median, minimum and maximum). Summary statistics for categorical variables will include frequency counts and percentages.

12.4 Analysis Populations

The safety analysis set consists of all randomized subjects who have received at least one dose of study medication, i.e., any dose of IDN-6556 or placebo. If the application of any study medication is not certain, the subject will be included in the safety analysis set. The analyses based on the safety analysis set will be conducted on an “as treated” basis, i.e., all subjects will be analyzed by the treatment they have actually received.

Title: A Multicenter, Double-Blind, Randomized Trial of IDN-6556 in Subjects Who had Hepatitis C Virus (HCV) Reinfection and Liver Fibrosis or Cirrhosis following Orthotopic Liver Transplantation for Chronic HCV Infection and Who Subsequently Achieved a Sustained Virologic Response Following anti-HCV Therapy

The Full Analysis Set (FAS) population consists of all randomized subjects who have received at least one dose of study medication, i.e., any dose of IDN-6556 or placebo. The analyses based on the FAS population will be conducted on an intention-to-treat (ITT) principle (i.e., all subjects will be analyzed with the group to which they were randomly assigned).

The Per Protocol (PP) population will be used as a sensitivity analysis of the primary endpoint. Criteria for assessing the PP population will be detailed in the Statistical Analysis Plan (SAP).

All safety analyses will be based on the safety analysis set. All efficacy analyses will be based on the intention-to-treat population

12.5 Sample Size

The sample size determination for this study is based on the Phase 2b screening methodology presented in Fleming and Richardson¹².

A total of 60 subjects will be treated in a 2:1 ratio to IDN-6556 or placebo. Treatment duration for all subjects will be two years. The primary outcome variable is change in Ishak Fibrosis Score at 24 months.

The primary analysis of this Phase 2 “screening” study is formally based on a three-category decision guideline. To be specific, the decision guideline for this study is based on whether the proportion of subjects who show a regression (i.e., improvement) of Ishak Fibrosis Score at 24 months for the IDN-6556 arm compared to the placebo arm is less than 5%, is from 5% up to 15%, or is at least 15%.

Note that these categories should not be interpreted as providing strict decision rules but rather as guidelines that will be factored into a broader scientific assessment of the benefit to risk profile of the IDN-6556 regimen. This broader assessment will include consideration of safety, of secondary efficacy endpoints, and of relevant information external to this study. Specifically, the decision guidelines for this study are:

1. If the estimated absolute increase in the proportion of subjects who show regression in Ishak Fibrosis Score is less than 5%, (e.g., less than an estimated increase from 30% to 35%), then the IDN-6556 regimen is not plausibly more efficacious than placebo; the formulation of this IDN-6556 regimen or its utility in this indication will be reconsidered.
2. If the estimated absolute increase in the proportion of subjects who show regression in Ishak Fibrosis Score is from 5% up to 15%, (e.g., an estimated increase from 30% to between 35% and 45%), then the IDN-6556 regimen is

Title: A Multicenter, Double-Blind, Randomized Trial of IDN-6556 in Subjects Who had Hepatitis C Virus (HCV) Reinfection and Liver Fibrosis or Cirrhosis following Orthotopic Liver Transplantation for Chronic HCV Infection and Who Subsequently Achieved a Sustained Virologic Response Following anti-HCV Therapy

plausibly more efficacious than placebo and if analyses of biomarkers suggest utility of the IDN-6556 regimen, should be evaluated definitively in a subsequent Phase 3 clinical study.

3. If the estimated absolute increase in the proportion of subjects who show regression in Ishak Fibrosis Score is at least 15%, (e.g., an estimated increase from 30% to greater than 45%), then the IDN-6556 regimen will be evaluated definitively in a subsequent Phase 3 study.

The operating characteristics for this three-category decision guideline (based on 100,000 simulated trials) are shown in the table below.

Table 12.1 Probabilities of Study Outcomes According to Various Levels of True Treatment Effect (TE)

| TE | Probability of obtaining an estimated TE (active – placebo) | | |
|----|---|-----------------|------|
| | <5% | Of >5% but ≤15% | >15% |
| 0 | 67% | 22% | 11% |
| 5 | 52% | 26% | 22% |
| 10 | 36% | 27% | 37% |
| 15 | 23% | 24% | 53% |
| 20 | 13% | 19% | 68% |
| 25 | 7% | 13% | 80% |
| 30 | 3% | 8% | 89% |

Of note:

1. The false-positive error rate of the screening procedure is low. In particular, if the IDN-6556 regimen truly provides no improvement in the 2-year Ishak Fibrosis Score, then there is only an 11% chance of going forward to a Phase 3 study and only a 2.5% chance of false positive conclusion that the IDN-6556 regimen has statistically significant improvement in efficacy relative to placebo.
2. The false-negative error rate is acceptable. If the IDN-6556 regimen truly provides an absolute increase of 15%, (e.g., an increase from 30% to 45%), then there is only a 23% chance that the combination intervention would be discarded, and thus a 77% chance that it would be evaluated in a subsequent Phase 3 study. If the true absolute increase is 15%, there is a 20% chance that the IDN-6556 regimen will have a statistically significant improvement in efficacy relative to placebo and a 80% chance of a statistically significant difference if the true absolute increase is 37% (at the 2-sided 0.05 level).

Title: A Multicenter, Double-Blind, Randomized Trial of IDN-6556 in Subjects Who had Hepatitis C Virus (HCV) Reinfection and Liver Fibrosis or Cirrhosis following Orthotopic Liver Transplantation for Chronic HCV Infection and Who Subsequently Achieved a Sustained Virologic Response Following anti-HCV Therapy

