4 PLANNED SIZE DETERMINATION

This study will be conducted at multiple centers at which approximately 60 subjects will be enrolled and treated in a 2:1 ratio with emricasan or placebo, respectively. The sample size determination for this study is based on the Phase 2b screening methodology presented in [Fleming and Richardson \(2004\)](#).

The base case for the placebo response rate of 30% was assumed and obtained from [George, et al \(2009\)](#), where it stated that 29% of patients showed a response in fibrosis from a mean of 1.6 years following HCV-SVR.

Treatment duration for all subjects is expected to be two years. The primary analysis of this Phase 2 “screening” study is formally based on a three-category decision guideline. The decision guideline for this study is based on whether the difference in the proportions of subjects who show a response (i.e., improvement or no change) per their Ishak Fibrosis Score at 24 months for emricasan compared to placebo is less than 5%, is from 5% up to 15%, or is more than 15%. Specifically, the outcome of the study will determine one of the following three course of action:

1. If the difference in response rates between emricasan and placebo (i.e., emricasan response rate – placebo response rate) is less than 5%, then emricasan regimen is not plausibly more efficacious than placebo; hence, emricasan or its utility in this indication will be reconsidered.
2. If the difference in response rates between emricasan and placebo is from 5% up to 15%, then emricasan is plausibly more efficacious than placebo in this indication if secondary analyses of biomarkers suggest utility of emricasan or a positive safety profile is observed; hence, emricasan could be evaluated in a subsequent Phase 3 clinical study.
3. If the difference in response rates between emricasan and placebo is more than 15%, then emricasan could be evaluated in a subsequent Phase 3 study.

These categories should not be interpreted as providing strict decision rules but rather as guidelines that will be factored into a broader scientific assessment of the benefit to risk profile for emricasan in this indication. This broader assessment will include consideration of secondary efficacy analyses, safety profile, and relevant information external to this study.

The operating characteristics for this three-category decision guideline are shown in Table 1.

Table 1. Operating Characteristics for Three-Category Decision Guideline

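### Protocol 12.5 quotes its 11% and 77% go-forward chances on different counts of category 2, and the 5% and 15% cut-offs are worded four ways over one set of probabilities

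*Protocol*

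**What the plan says.** Protocol 12.5 sorts the trial result into three categories by the estimated difference in regression rates. Category 1 leads to reconsideration. Category 2 leads to Phase 3 "if analyses of biomarkers suggest utility of the IDN-6556 regimen". Category 3 leads to Phase 3 with no such condition. SAP 4 keeps the three categories but lets category 2 qualify "if secondary analyses of biomarkers suggest utility of emricasan or a positive safety profile is observed", and softens category 3: if the difference "is more than 15%, then emricasan could be evaluated in a subsequent Phase 3 study".

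Two notes under Table 12.1 summarise the error rates. Note 1 calls the false-positive rate low: with no true effect, "then there is only an 11% chance of going forward to a Phase 3 study". Note 2 calls the false-negative rate acceptable: at a true increase of 15 points, "there is only a 23% chance that the combination intervention would be discarded, and thus a 77% chance that it would be evaluated" in Phase 3.

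The cut-offs (in percentage points) read as follows:

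| Place | Bottom | Middle | Top |
|---|---|---|---|
| Protocol 12.5 text | <5 | 5 up to 15 | ≥15 |
| Protocol Table 12.1 | <5 | >5 to ≤15 | >15 |
| SAP 4 text | <5 | 5 up to 15 | >15 |
| SAP Table 1 | ≤5 | 5 to <15 | ≥15 |

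The protocol text is "is less than 5%, is from 5% up to 15%, or is at least 15" per cent; the SAP text is "is less than 5%, is from 5% up to 15%, or is more than 15" per cent. Protocol category 3 also mixes two rules within one sentence: "is at least 15%, (e.g., an estimated increase from 30% to greater than 45" per cent. Both tables print the same 21 probabilities.

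**The concern.** The two notes are meant to be read together, as the price and the benefit of the screening rule. If the narrow count is used for the false-positive side and the wide count for the false-negative side, each error rate appears at its more favourable value. A reader weighing 11% against 77% sees a sharper rule than the table shows on either single count.

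The cut-offs matter because the estimate is discrete. With 40 and 20 subjects the difference moves in steps of 2.5 points, so 5% and 15% are both attainable values. Under Table 12.1 an estimate of exactly 5% has no column; under SAP Table 1 it has two. An estimate of exactly 15% is top category in the protocol text and in SAP Table 1, and middle category in Table 12.1 and the SAP text. Protocol 12.5 says the primary analysis is formally based on this guideline. SAP 9.1 sets study success by cross-reference to criteria (printed as Section 0, presumably SAP 4).

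**Working it through.** **Inputs.** 40 active and 20 placebo subjects (Protocol synopsis and Table 7.1); 30% placebo response (an example in Protocol 12.5, the base case in SAP 4); the printed rows of Table 12.1: 67/22/11 at a true effect (TE) of 0 and 23/24/53 at TE 15.

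**Step 1: reproduce the two quoted figures.** The 11% is the top cell at TE 0. The 77% is 100 − 23 = 24 + 53 at TE 15, so it includes all of category 2.

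**Step 2: put both on one basis.** Let q be the chance that the category 2 condition is met. Then P(go forward) = category 3 + q × category 2.

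- TE 0: 11 + 22q
- TE 15: 53 + 24q
- q = 0 in both rows: 11% against 53% (lower bounds)
- q = 1 in both rows: 33% against 77% (upper bounds)
- The quoted 11% and 77% need q = 0 at TE 0 and q = 1 at TE 15.

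Neither document gives a value for q, so 33% and 77% should carry the words up to.

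**Step 3: how often the boundaries matter.** All 41 × 21 outcome pairs were enumerated from two independent binomials (40 at 0.30 + TE, 20 at 0.30), with integer comparison of the difference against 5% and 15%.

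| TE | exactly 5% | exactly 15% | either, about |
|---|---|---|---|
| 0 | 7.4% | 4.0% | 11% |
| 5 | 7.8% | 5.9% | 14% |
| 10 | 7.1% | 7.3% | 14% |
| 15 | 5.6% | 7.7% | 13% |
| 20 | 3.8% | 7.0% | 11% |

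**Step 4: try each rule against the printed table.**

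| Rule, ties handled exactly | TE 0 | TE 15 |
|---|---|---|
| Printed | 67/22/11 | 23/24/53 |
| <5, 5 to <15, ≥15 (Protocol text) | 61.2/25.1/13.6 | 19.1/26.4/54.4 |
| <5, 5 to 15, >15 (SAP text) | 61.2/29.2/9.6 | 19.1/34.1/46.8 |
| ≤5, >5 to 15, >15 (Table 12.1, with 5% put in the bottom column) | 68.7/21.7/9.6 | 24.7/28.5/46.8 |
| ≤5, >5 to <15, ≥15 (SAP Table 1, with 5% put in the bottom column) | 68.7/17.7/13.6 | 24.7/20.8/54.4 |

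Putting 5% in the middle column of SAP Table 1 gives the Protocol-text row. After rounding, the four rules match 2, 0, 1 and 1 of the 21 printed cells.

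**Step 5: sensitivity to arm size.** Over all 45 pairs from 34–42 active by 17–21 placebo, with the Protocol-text rule, categories 2 or 3 together run 31.8–38.8% at TE 0 and 74.5–80.9% at TE 15. The printed 33 and 77 lie inside these ranges. No pair brings the wide count under no effect near 11%.

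**Step 6: the notes' other figures.** A pooled z-test at two-sided 0.05 gives 2.4% in favour of the drug at TE 0, 20.3% power at +15 and 80.3% at +37. The stated 2.5%, 20% and 80% reproduce.

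**The case against.** A reader might infer that 11% and 77% cannot both hold under any single rule. The protocol does not support that. Category 2 goes forward only if the biomarkers agree; if biomarkers separated inactive from active drug perfectly, the one written rule would give exactly 11% and 77%. What remains is that this is the most favourable possible assumption and it is not stated.

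It is also fair to say that both documents call the categories guidelines rather than strict rules, that every cell needed to see the 33% is printed above the notes, and that the SAP does not repeat the 11%, the 77% or the word low. This limits the consequence, but it does not put the two notes on the same count. Protocol 12.1 allows the SAP to modify the protocol. That could explain a different SAP rule, but not a conflict between each document's text and its own table, and SAP 14.1 lists no change of cut-offs.

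On the table, a reader might infer a proven programming error. Ordinary double-precision comparison (below 0.05, above 0.15) at 40/20 and 30% placebo does match all 21 cells, which suggests that rounding error split the ties. No passage describes the code, so this stays an inference. The tie frequencies also assume complete data: SAP 9.1 combines multiply imputed datasets, and with missing Month 24 biopsies the estimate would land exactly on a cut-off less often.

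Finally, whether a 30% placebo rate fits the SAP definition of response, which counts stable F2–F5 subjects, is a separate question. Any other rate is an assumption. At 40/20 with the Protocol-text rule, assumed placebo rates from 20% to 80% move the categories 2-or-3 figure at +15 between 79.7% and 88.3%, but leave category 3 at 53.6–55.1%.

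**Conclusion.** The point holds as a misstatement of the screening rule's error rates, not as a fault in the trial's conduct or testing. From printed cells alone, the chance of going forward is 11% to at most 33% under no effect and 53% to at most 77% at +15, depending on how often the category 2 condition is met. On the count that gives the 77%, an inactive drug escapes discard in a third of trials, three times the 11% quoted. The 33% is an upper bound and should not be read as the false go-forward rate itself. Nor does the 2.5% in note 1 answer the point: it is the rate of a significant result, and the guideline uses no significance test.

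The boundary conflict is plain on the page. Its size, about 11–14% of trials on a tie for true effects of 0 to 20 points and cell shifts of about 4 to 8 points at TE 0 and 15, rests on complete 40/20 outcomes and 30% placebo response. Under those inputs no stated rule reproduces the table with exact ties; why it does not cannot be established from the documents.

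**What to change.** (a) Restate notes 1 and 2 as matched pairs from the same columns: 11% to at most 33% under no effect, and 53% to at most 77% at +15. Say that category 2 is conditional, with each document's own condition (biomarkers in the protocol; biomarkers or a positive safety profile in the SAP), and drop the word low.

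(b) Use one boundary rule in the Protocol 12.5 text, Table 12.1, the SAP 4 text and SAP Table 1, and correct the category 3 example to match. If the SAP rule is meant to differ, list the change in SAP 14.1.

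(c) Recompute the table under that rule with integer counts. State that it assumes complete 40/20 outcomes and 30% placebo response and does not describe the multiply imputed estimate of SAP 9.1. Then update the pairs in (a). As an example only, the Protocol-text rule would give category 3 as 13.6% against 54.4%, and categories 2 or 3 as at most 38.8% (25.1 + 13.6, before rounding) against at most 80.9% (26.4 + 54.4, before rounding).

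The cost is text edits to the notes and the cut-off wording in both documents, an entry in SAP 14.1 if needed, and one recalculated table. The stated false go-forward rate becomes less favourable. Sample size, conduct and testing are untouched.
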